2.2 General definitions

Study drug and study treatment

Study drug and study treatment refer to LTT462 and are used interchangeable.

Date of first/last administration of study drug and study treatment

The date of first (last) administration of study treatment is derived as the first (last) date when a non-zero dose of study treatment LTT462 was administered and recorded on the Dosage Administration Record panel. For the sake of simplicity, the date of first (last) administration of study treatment will also be referred as start (last) date of study treatment.

Study day

The study day for all assessments/onset of events will be calculated using the start date of study treatment as reference. For assessments/events occurring on or after the start date of study treatment, study day will be calculated as:

Novartis	Confidential	Page 8
SAP	13-May-2019 (11:03)	CLTT462X2101

Study day (days) = Event date - Start date of study treatment + 1

Therefore, the first day of study treatment is study day 1.

For all assessment/onset of events occurring prior to the start of the study treatment, study day will be negative and will be calculated as:

Study day (days) = Event date – Start date of study treatment

On-treatment assessment/event

An on-treatment assessment/event is defined as any assessment/event in the time interval from the start date of LTT462 treatment until the last date of LTT462 treatment + 30 days inclusive.

LTT462 dose interruption

Study drug dose interruption is defined as a "total daily dose" equal to zero, between the first and last non-zero doses, following a non-zero total daily dose. This applies to any regimen, in our case QD and independently of the reason for interruptions.

LTT462 dose reduction

Time points at which the dose change flag is checked and the total daily dose is nonzero.

If the total daily dose at that time point is lower than the total daily dose at the time that the last non-zero dose was administered then the dose change is identified as a dose reduction.

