2.2 Rationale for the study design

The design of the phase I, open label, dose finding study, with a dose escalation part and a dose expansion part, was chosen in order to establish the safety and tolerability of LTT462 and identify a recommended dose and regimen for future studies in adult and adolescent patients with advanced solid tumors harboring documented MAPK pathway alterations.

The age of patients eligible for inclusion in this study is ≥ 12 years to allow access to LTT462 treatment for adolescent patients with MAPK pathway alterations who have the same risk/benefit as the adult population. [REDACTED]

[REDACTED] The inclusion of patients ≥ 12 years is supported by published literature showing that adolescents have similar toxicity profiles, maximum tolerated doses, and pharmacokinetic parameters compared to adults.

The statistical analysis of the primary endpoints other than incidence of dose limiting toxicities (DLTs) during the dose escalation part [REDACTED] will be descriptive ([Section 10.4.2.1](#)). No hypotheses or models will be considered. Incidence of DLTs during the dose escalation part will be analyzed using an adaptive Bayesian model. Sample size requirements are provided in [Section 10.8](#).

Dose Escalation Part

[figure not shown]
[figure not shown]
All patients enrolled during the dose escalation part of the study, will receive LTT462 in order to evaluate its safety and tolerability. On C1D1 only 1 dose will be given (in the morning) for all regimens. The evening dose on C1D1 will be omitted for the BID regimen. In addition, dosing will be omitted on the second day of the first cycle (C1D2; a cycle is defined as 28 days) for all regimens. This is to allow for a 48 hour sampling to fully characterize LTT462 PK parameters, such as total plasma exposures (AUC_{inf}) and $T_{1/2}$, and PD.

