6.1.1 Dosing regimen

Table 6-1 Dose and treatment schedule

[figure not shown]
Study treatments	Pharmaceutical form and route of administration	Dose	Frequency and/or Regimen*
LTT462	Capsule for oral use	As assigned	Daily **

* If emerging PK and/or safety data indicate that this regimen is not optimal, the Novartis Clinical Study team may recommend an alternative dosing regimen in the treatment period for newly enrolled patients such as [REDACTED], BID [REDACTED] (Section 4.1).

** Study treatment will be omitted on C1D2 of the treatment period for all dosing regimens, see Section 4.1 or Table 7-1. Additionally the C1D1 evening dose will be omitted for BID dosing.

LTT462 should be taken as follows:

[figure not shown]
- LTT462 will be administered orally at flat-fixed doses (not by body weight or body surface area).
- Adolescent patients will be treated with the same dose as adult patients (see Section 2.3).
- Patients should take their dose at approximately the same time [REDACTED] on each day of dosing with a glass of water [REDACTED]
- Study treatment should be taken in the morning (for BID dosing, the study treatment should be taken in the morning and in the evening. [REDACTED])
- The C1D2 should be omitted for all dosing regimens. Additionally the C1D1 evening dose should be omitted for the BID regimen.
- On the days of PK sampling, the patients should take their doses in the clinic where the administration of LTT462 will be supervised and administration time recorded.
- The capsules should be ingested whole and should not be chewed or crushed.
- If multiple capsules are required for a dosage, then all capsules for that dose should be ingested in a short period of time as possible (i.e., not slower than 1 capsule every 2 minutes).

- If vomiting occurs following the dosing of study treatment, re-dosing is not permitted and dosing should resume at the next scheduled dose. If the vomiting occurs on full PK sampling days within the first 4 hours post-dosing, this event should be recorded on the dose administration PK electronic Case Report Form (eCRF) page, as well as on the adverse event page, as appropriate.
- If the patient forgets to take the scheduled dose and more than 4 hours has passed since the scheduled time of study treatment intake, that dose should be skipped and treatment should continue with the next scheduled dose at the prescribed level (missed doses should not be replaced or made up at the next scheduled dosing).

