10.1.4 Dose-determining analysis set

The DDS includes all patients from the Safety Set (escalation part) who met the minimum exposure criterion and had sufficient safety evaluations, or experienced a DLT during the first 28 days of dosing.

A patient has met the minimum exposure criterion when exposed to the received study treatment (as defined in the Safety Set definition above) for at least 75% of the planned LTT462 total daily doses in the first cycle of treatment.

- For QD: at least 75% percent of the planned daily doses means at least 21/27, given that the C1D2 dose will be omitted.

[figure not shown]
- For BID: at least 75% of planned BID daily doses means at least 20/26 full days of dosing of the planned doses, given the C1D2 dose will be omitted and a single dose will be administered on the first day of treatment.

Patients who do not experience a DLT during the first cycle of dosing are considered to have sufficient safety evaluations if they have been observed for ≥ 28 days following the first dose, and are considered by both the Sponsor and Investigators to have enough safety data to conclude that a DLT did not occur.

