1.2 Study objectives and endpoints

Table 1-1 Primary and secondary objectives

Objective	Endpoint
Primary	
To characterize safety and tolerability of LTT462 and identify a recommended dose and regimen for future studies in adult patients with advanced solid tumors harboring MAPK pathway alterations.	Safety: Incidence and severity of adverse events (AEs) and serious AEs (SAEs), including changes in laboratory values, vital signs, and ECGs.
	Incidence and nature of DLTs (dose escalation only)
	Tolerability: Dose interruptions, reductions, and dose intensity
Secondary	
To evaluate the preliminary anti-tumor activity of LTT462	For both parts: Overall response rate (ORR), Disease Control Rate (DCR), Duration of Response (DOR), and Progression Free Survival (PFS) as per Response Evaluation Criteria in Solid Tumors (RECIST) version 1.1
To evaluate the pharmacokinetic (PK) profile of LTT462	Plasma concentrations and derived PK parameters of LTT462
To assess the pharmacodynamic (PD) effect of LTT462	Changes from baseline of the PD marker DUSP6 in tumor tissue and in blood.

2 Statistical Methods

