2.3 Analysis sets

Full Analysis Set (FAS)

The FAS will be the default to be used for all efficacy analyses. Listings of raw data will use the FAS, unless otherwise noted. It includes all patients who received at least one dose of study drug (full or partial). Patients will be classified according to the planned (i.e., assigned) treatment (dose level, regimen, _____).

Safety Set

The safety set will be the primary population for all safety related endpoints except determination of the dose-DLT relationship. It includes all patients who received at least one dose (full or partial) of study treatment. The statement that a patient did not experience an adverse event constitutes a valid safety assessment. Patients will be analyzed according to the treatment received, where treatment received is defined as:

- The treatment assigned, if it was received at least once, or
- The first study treatment received, if the treatment assigned was never received.

Dose-determining Set

The DDS consists of all patients from the safety set in the dose escalation part of the trial who either meet the following minimum exposure criterion and have sufficient safety evaluations

Novartis	Confidential	Page 9
SAP	13-May-2019 (11:03)	CLTT462X2101

during the first 28 days of dosing or discontinue earlier due to a DLT during the first 28 days of dosing. This constitutes an evaluable patient for the determination of MTD. Patients in the DDS will be identified prior to each dose escalation meeting and will be confirmed prior to database lock.

In this study, if data on AEs, vital signs, Labs, and dose administration is collected at least at study visits C1D1, C1D8 and C1D15, patient is considered as having sufficient safety evaluations. The statement that a patient did not experience an adverse event constitutes a valid safety assessment.

A patient is considered to have met the minimum exposure requirement if they have received at least 75% of the planned doses of each of the assigned combination drugs during the first cycle (the first 28 days of dosing). For all regimens proposed this equates to at least 21 of the planned 28 doses LTT462.

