2.12 Tolerability

Tolerability of study drug treatment will be assessed by summarizing the number and percentage of dose interruptions and dose reductions per patient, together with reasons for dose interruption and dose reductions. Dose intensity and relative dose intensity of LTT462 per patient will be summarized. For relative dose intensity, the number and proportion of patients

Novartis	Confidential	Page 20
SAP	13-May-2019 (11:03)	CLTT462X2101

within the following categories will be presented: $< 0.5, \ge 0.5 - < 0.75, \ge 0.75 - < 0.9, \ge 0.9 - < 1.1$ and ≥ 1.1 .

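### The SAP's dose-interruption rule counts the planned no-dose day C1D2, so every patient dosed on or after C1D3 is reported as interrupted

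*SAP*

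**What the plan says.** **Definition.** SAP 2.2 calls it an interruption when the total daily dose is "equal to zero, between the first and last non-zero doses, following a non-zero total daily dose". It applies this to any regimen "and independently of the reason for interruptions". The visible text makes no exception for days on which no dose was planned.

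**Planned schedule.** Protocol 2.2 states that "dosing will be omitted on the second day of the first cycle", and the footnote to Table 6-1 in protocol 6.1.1 repeats it: "Study treatment will be omitted on C1D2 of the treatment period for all dosing regimens". Protocol 4.1.1 gives the same reason, PK and PD sampling over 48 hours. C1D1 is a dosing day under every regimen; for BID only the morning dose is given.

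**Use of the result.** SAP Table 1-1 lists "Tolerability: Dose interruptions, reductions, and dose intensity" under the primary objective. SAP 2.12 will assess tolerability by "summarizing the number and percentage of dose interruptions and dose reductions per patient", with reasons. SAP 2.1 sets outputs out by treatment group.

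**A related count.** For the dose-determining set, SAP 2.3 says of the minimum exposure rule: "For all regimens proposed this equates to at least 21 of the planned 28 doses LTT462". Protocol 10.1.4 says for QD: "at least 75% percent of the planned daily doses means at least 21/27, given that the C1D2 dose will be omitted". For BID it gives 20 of 26 full days.

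**The concern.** C1D2 is a zero-dose day by design, and it lies between two dosing days for any patient who continues to C1D3. Read literally, the SAP rule scores this planned PK omission as an interruption. Because the rule disregards the reason, the omission cannot be read out of it.

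What is at stake is a primary tolerability summary. The percentage of patients with any interruption would not separate one dose group from another, and patients who took every scheduled dose would be reported as interrupted. The exposure rule in SAP 2.3 shows the same oversight: it counts 28 planned doses, where the protocol removes C1D2 from the denominator.

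**Working it through.** **1. The protocol's own figures that rest on C1D2.** The cycle is 28 days and the threshold is 75% (protocol 10.1.4, SAP 2.3).

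- QD: 28 − 1 = 27 planned days; 0.75 × 27 = 20.25, rounded up to 21; 21/27 = 77.8%. Matches the protocol.
- BID: 28 − 2 = 26 full days; 0.75 × 26 = 19.5, rounded up to 20; 20/26 = 76.9%. Matches the protocol.
- SAP, all regimens: 0.75 × 28 = 21; 21/28 = 75.0%. C1D2 is not removed.

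So the protocol treats C1D2 as unplanned for dosing, and the SAP does not. Neither document states an interruption rate to reproduce.

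**2. C1D2 against the SAP 2.2 definition.** The total daily dose is zero (met). It follows a non-zero dose on C1D1 (met). It precedes the last non-zero dose (met by anyone dosed on or after C1D3). The reason is irrelevant under the rule.

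**3. Rule applied to a 28-day cycle with C1D2 = 0.** Each run of consecutive zero-dose days counts once.

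| Pattern | SAP rule | C1D2 excluded |
|---|---|---|
| Fully compliant, QD | 1 | 0 |
| Fully compliant, BID | 1 | 0 |
| Misses C1D10 only | 2 | 1 |
| Misses C1D10 to C1D12 | 2 | 1 |
| Misses C1D3 only | 1 | 1 |
| Dosed on C1D1 only | 0 | 0 |

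**4. Percentage with any interruption.** Let *q* be the share of patients with no dose on or after C1D3, and *t* the true rate of unplanned interruption among the rest. The documents give neither, so both are assumed over a range.

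- SAP rule: 1 − *q*, which does not contain *t*.
- C1D2 excluded: *t* × (1 − *q*).

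| True rate *t* | SAP rule, *q* = 0 | Excluded, *q* = 0 | SAP rule, *q* = 5% | Excluded, *q* = 5% |
|---|---|---|---|---|
| 0% | 100% | 0% | 95% | 0% |
| 10% | 100% | 10% | 95% | 9.5% |
| 30% | 100% | 30% | 95% | 28.5% |
| 50% | 100% | 50% | 95% | 47.5% |
| 80% | 100% | 80% | 95% | 76% |

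One patient dosed on C1D1 only lowers the SAP figure to 2/3 = 66.7%, 5/6 = 83.3% or 20/21 = 95.2% in groups of 3, 6 and 21. That fall reflects early stopping and says nothing about *t*.

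**5. Counts.** Take two groups of 6 with one single unplanned interruption, not adjoining C1D2, in 1 and in 4 patients (assumed). The SAP rule gives 6 + 1 = 7 and 6 + 4 = 10 interruptions, against true counts of 1 and 4. The difference of 3 is kept. In a simulation of 20,000 patients per scenario, with at most one unplanned run of 1 to 3 days each, mean counts under the SAP rule were 1.00, 1.09, 1.29, 1.48 and 1.65 at true rates of 0%, 10%, 30%, 50% and 67%. Counts therefore still rise with the true rate, while the percentage with any interruption stayed at 100% throughout.

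**The case against.** The strongest reply is that the 100% is a prediction about output nobody has seen. Neither document says whether C1D2 is entered as a zero-dose record on the dosage administration form, and the programming specifications and table shells, which could handle the gap, are not available. Text may also have been blacked out after the mention of QD in the definition. This limits certainty about the final tables. It does not rescue the wording: the rule turns on the total daily dose, which is zero on C1D2 however it is recorded, and the visible sentence covers any regimen and any reason. A specification that exempted C1D2 would depart from the SAP's stated definition.

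Second, SAP 2.12 does not define the percentage as patients with any interruption. That is the natural reading, but it is an inference. The counts are also inflated, usually by one per patient.

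Third, the planned summary of reasons and the dosing listing would probably expose a universal day-2 gap. That is fair, but the headline percentage would remain uninformative.

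Fourth, the exposure mismatch concerns a different analysis set, and for QD the required number is 21 in both documents, so no QD patient changes status. This stands. It is a separate inconsistency with the same origin and does not itself prove the interruption defect.

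Finally, one can argue that the point is minor, since the analysis is descriptive and the distortion is at most one known event per patient. Those limits are real. Even so, a stated rule gives a wrong result on a named primary endpoint.

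**Conclusion.** The concern holds, and the point should be fixed. As written, SAP 2.2 gives one interruption to every fully compliant patient dosed on or after C1D3, and the percentage with any interruption among such patients is 100% at every true rate. This assumes that C1D2 is not dosed by deviation, that its total daily dose is derived as zero, that no exemption sits in text we cannot see, and that the percentage is of patients with any interruption.

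The consequence is confined to the descriptive interruption summary. Differences in counts and the summary of reasons stay partly informative. Dose reductions are unaffected, and no stated escalation rule uses the percentage.

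**What to change.** In SAP 2.2, define an interruption as a zero total daily dose on a day when dosing was scheduled per protocol. Exclude C1D2 and any other planned zero-dose day. Count consecutive unplanned zero-dose days as one interruption, and say that a run starting directly after C1D2 still counts, so that a missed C1D3 is not lost. Carry the same wording into the programming specifications.

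Separately, reconcile the 21 of 28 planned doses in SAP 2.3 with the 21/27 (QD) and 20/26 full days (BID) in protocol 10.1.4, and state whether the unit is doses or days.

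The cost is wording in the SAP and the specifications. No new data are needed and no dosing rule changes. SAP section 1 already provides the route: an amendment before database lock or an addendum after it.

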2.3 Analysis sets

Full Analysis Set (FAS)

The FAS will be the default to be used for all efficacy analyses. Listings of raw data will use the FAS, unless otherwise noted. It includes all patients who received at least one dose of study drug (full or partial). Patients will be classified according to the planned (i.e., assigned) treatment (dose level, regimen, _____).

Safety Set

The safety set will be the primary population for all safety related endpoints except determination of the dose-DLT relationship. It includes all patients who received at least one dose (full or partial) of study treatment. The statement that a patient did not experience an adverse event constitutes a valid safety assessment. Patients will be analyzed according to the treatment received, where treatment received is defined as:

- The treatment assigned, if it was received at least once, or
- The first study treatment received, if the treatment assigned was never received.

Dose-determining Set

The DDS consists of all patients from the safety set in the dose escalation part of the trial who either meet the following minimum exposure criterion and have sufficient safety evaluations

Novartis	Confidential	Page 9
SAP	13-May-2019 (11:03)	CLTT462X2101

during the first 28 days of dosing or discontinue earlier due to a DLT during the first 28 days of dosing. This constitutes an evaluable patient for the determination of MTD. Patients in the DDS will be identified prior to each dose escalation meeting and will be confirmed prior to database lock.

In this study, if data on AEs, vital signs, Labs, and dose administration is collected at least at study visits C1D1, C1D8 and C1D15, patient is considered as having sufficient safety evaluations. The statement that a patient did not experience an adverse event constitutes a valid safety assessment.

A patient is considered to have met the minimum exposure requirement if they have received at least 75% of the planned doses of each of the assigned combination drugs during the first cycle (the first 28 days of dosing). For all regimens proposed this equates to at least 21 of the planned 28 doses LTT462.

Patients who do not experience a DLT during the first 28 days of dosing are considered to have sufficient safety evaluations if they have been observed for 28 days or more following the first dose, and are considered by both Novartis and Investigators (at the dose escalation meetings) to have enough safety data to conclude that a DLT did not occur.

PK analysis set for the treatment period

The Pharmacokinetic Analysis Set (PAS) includes all patients who have at least one PK blood sample providing measurable LTT462 and who satisfy the bullets below:

- received at least one dose of LTT462,
- patient provided at least one primary PK parameters,
- patient did not vomit within 4 hr of dose administration,

The PAS will be used for summaries of PK data (tables and figures) as well as for listings of derived parameters.

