Medication number	A unique identifier on the label of each study treatment package which is linked to one of the treatment groups of a study
Other study treatment	Any drug administered to the patient as part of the required study procedures that was not included in the investigational treatment
Subject Number (Subject No.)	A unique identifying number assigned to each subject who enrolls in the study
Period	A subdivision of the study timeline; divides stages into smaller functional segments such as screening, baseline, titration, washout, etc.
Stage related to study timeline	A major subdivision of the study timeline; begins and ends with major study milestones such as enrollment, randomization, completion of treatment, etc.
Stage in cancer	The extent of a cancer in the body. Staging is usually based on the size of the tumor, whether lymph nodes contain cancer, and whether the cancer has spread from the original site to other parts of the body
Stop study participation	Point/time at which the patient came in for a final evaluation visit or when study treatment was discontinued whichever is later
Study treatment	Includes any drug or combination of drugs in any study arm administered to the patient (subject) as part of the required study procedures, including placebo and active drug run-ins. In specific examples, it is important to judge investigational treatment component relationship relative to a study treatment combination; study treatment in this case refers to the investigational and non-investigational treatments in combination.
Study treatment discontinuation	Point/time when patient permanently stops taking study treatment for any reason
Supportive treatment	Refers to any treatment required by the exposure to a study treatment, e.g. premedication of vitamin supplementation and corticosteroid for pemetrexed disodium.
Treatment group	A treatment group defines the dose and regimen or the combination, and may consist of 1 or more cohorts. Cohorts are not expanded, new cohorts are enrolled.
Variable	Identifier used in the data analysis; derived directly or indirectly from data collected using specified assessments at specified time points
Withdrawal of Consent	Withdrawal of consent occurs only when a patient does not want to participate in the study any longer, and does not want any further visits or assessments, and does not want any further study related contact

Amendment 3 (13-Mar-2018)

Amendment rationale

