6.2.3.2 Dose cohort modification

For the purposes of dose escalation decisions, each cohort will consist of 1 to 6 newly enrolled patients who will be treated at the specified dose level. The first cohort will be treated with the starting dose of 45 mg QD.

Patients must complete a minimum of 1 cycle of treatment with the minimum safety evaluation and drug exposure or have had a DLT within the first cycle of treatment to be considered evaluable for dose escalation decisions ([Section 10.1.4](#)). Dose escalation decisions will occur when the cohort of patients has met these criteria.

If two patients (who may be in different cohorts) have experienced a toxicity of Common Terminology Criteria for Adverse events (CTCAE) grade 2, for which relationship to study drug cannot be ruled out; or when any single patient experiences a DLT or adverse event (AE) of CTCAE grade 3 or greater during Cycle 1, the cohort size will be increased to between 3 and 6 evaluable patients for the current and subsequent cohorts.

If a minimum of 3 patients are required in a cohort and only 2 of these patients are evaluable and neither subject has experienced a treatment-related toxicity > CTCAE grade 1, dose escalation decisions may be considered.

Dose escalation decisions will be made by the Investigators and Novartis study personnel. Decisions will be based on a synthesis of all relevant data available from all dose levels evaluated in the ongoing study including safety information, DLTs, all CTCAE Grade ≥ 2 toxicity data during Cycle 1, PK, and PD data from evaluable patients. The recommended dose for the next cohort of subjects will be guided by the BHLRM subject to the EWOC principle ([Section 10.4.2](#)).

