6.3 Dose modifications

6.3.1 Dose modification and dose delay

For patients who do not tolerate the protocol-specified dosing schedule due to DLT(s), dose adjustments are permitted in order to allow the patient to continue the study treatment. For the

[figure not shown]
dose escalation part of the study, dose reductions during Cycle 1 are only allowed if a DLT is observed and recorded.

[figure not shown]
The following guidelines need to be considered:

[figure not shown]
- The criteria for dose modifications and dose interruptions (i.e., interruption and re-initiation criteria for LTT462 treatment) for toxicities considered at least possibly related to the study treatment are outlined in [Table 6-4](#). All dose modifications should be based on the worst preceding toxicity (CTCAE version 4.03).
- A patient must discontinue treatment with LTT462 if, after treatment is resumed at a lower dose, the toxicity recurs with the same or worse severity, unless in the opinion of the investigator it is in the patient's best interest to continue LTT462, and upon documented agreement with Novartis.
- For each patient, once a dose level reduction has occurred, the dose level may not be re-escalated during subsequent treatment cycles with LTT462.
- If, due to study drug related toxicity, a patient requires a dose interruption of > 21 days from the intended day of the next scheduled dose, then the patient should be discontinued from the study treatment. However, if the patient with a dose interruption of > 21 days is clearly benefiting from the study treatment and in the opinion of the investigator it is in the patient's best interest to continue LTT462, upon documented agreement with Novartis, the patient may remain on study treatment. This decision must be available in the source documentation and described as an investigator comment in the eCRF.

[figure not shown]
In case of study treatment interruption, visit schedule should still be followed and assessments performed as per [Table 7-1](#).

[figure not shown]
Any dose modification and dose delay must be recorded on the Dosage Administration Record eCRF.

[figure not shown]

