2.3.1 Exclusion from analysis sets

In general, a patient must have provided written informed consent before inclusion into any analysis set, as specified in section 5.2 of the study protocol.

Table 2-2Reasons for excluding a patient from an analysis set

Analysis set	Deviation
Full analysis	Patient did not receive at least one dose of LTT462
Safety	Patient did not receive at least one dose of LTT462.
	Patient without at least one post-baseline safety assessment.

Novartis SAP	Confidential 13-May-2019 (11:03)	Page 10 CLTT462X2101
Analysis set	Deviation	
Dose-determining	Patient did not experience a DLT, however, the re exposure to the planned study treatment was not	
PK analysis,	If any of the conditions detailed above are violate from PAS	d, patient will be exclude

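### SAP 2.3 lets a DLT patient who misses the exposure or safety-evaluation criterion into the dose-determining set only if the DLT led to discontinuation; the protocol requires only that the DLT occurred

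*SAP*

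**What the plan says.** SAP 2.3 gives two routes into the DDS. The first is minimum exposure plus sufficient safety evaluations. The second is stopping because of a DLT. The operative words are "during the first 28 days of dosing or discontinue earlier due to a DLT during the first 28 days of dosing". The same paragraph says that this defines who is evaluable for the MTD, and that membership is settled before each dose escalation meeting and confirmed before database lock.

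The protocol's second route is wider. Section 10.1.4 ends its definition with "or experienced a DLT during the first 28 days of dosing". Section 6.2.3.2 likewise asks a patient either to complete a cycle with adequate exposure and evaluation or to "have had a DLT within the first cycle of treatment to be considered evaluable for dose escalation decisions". Neither mentions discontinuation.

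The protocol glossary defines study treatment discontinuation as "Point/time when patient permanently stops taking study treatment for any reason". SAP 2.2 defines a dose interruption separately, as a zero total daily dose between non-zero doses.

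The dose-determining row of SAP Table 2-2 (section 2.3.1), as far as it is legible, opens "Patient did not experience a DLT, however" and goes on to insufficient exposure. It therefore ties the low-exposure exclusion to patients without a DLT.

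**The concern.** The SAP adds a condition to the DLT route that the protocol does not have. A patient who has a DLT, pauses long enough to miss the exposure criterion and then resumes has not permanently stopped. Read literally, SAP 2.3 leaves that patient out.

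SAP 2.9.2.1 uses the DDS for the posterior DLT heatmap, the listing of model results at MTD declaration, and the DLT summary table and listing. These report a primary endpoint. SAP section 1 adds that the plan may serve as a reference for the MTD/RDE declaration.

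The error runs in one direction. The clause can remove only patients who had a DLT, so any effect makes the dose look less toxic. The one exception is a treatment group in which every patient had a DLT, where the rate stays at 100% or has no denominator.

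**Working it through.** **1. Can a DLT patient stay on treatment?** Protocol 6.3.1 says that after a DLT "dose adjustments are permitted in order to allow the patient to continue the study treatment". It directs discontinuation in two situations: where, because of drug-related toxicity, "a patient requires a dose interruption of > 21 days from the intended day of the next scheduled dose"; and where "after treatment is resumed at a lower dose, the toxicity recurs with the same or worse severity". Each has an exception agreed with the sponsor. A shorter interruption followed by resumption is therefore not a discontinuation.

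**2. Can that patient miss the exposure criterion?** For QD, the dose on Cycle 1 Day 2 is omitted (protocol 6.1.1).

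- Planned dosing days: Day 1 and Days 3 to 28, which is 1 + 26 = 27.
- Threshold: 0.75 × 27 = 20.25, rounded up to 21. This reproduces the 21/27 in protocol 10.1.4. The SAP writes the requirement as 21 of 28, so 21 doses is the QD requirement in both documents.
- Missing 7 doses leaves 27 − 7 = 20, which fails. Missing 6 leaves 21, which passes.

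Every single continuous interruption of 1 to 21 days starting on Day 3 to Day 28 was enumerated:

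| Interruption length | Start days that leave fewer than 21 doses |
|---|---|
| 1 to 6 days | none |
| 7 to 21 days | Days 3 to 22 (20 start days) |
| 7 to 21 days, starting Day 23 or later | none, because at most 6 dosing days of the cycle remain |

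Interruptions of 7 to 21 days do not reach the limit of more than 21 days in 6.3.1, so resuming is allowed.

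**3. The two rules applied to this patient** (QD, Cycle 1 DLT, 7-day interruption starting on Day 10, then resumed; 20 doses):

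| Rule | In the set? |
|---|---|
| Protocol 10.1.4 | Yes: a DLT occurred |
| Protocol 6.2.3.2 | Yes: evaluable |
| SAP Table 2-2, legible part | Not excluded: the reason listed is for patients without a DLT |
| SAP 2.3, literal | No: exposure missed and no permanent stop |

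**4. Illustration of size.** Take six evaluable patients with two DLTs and drop one DLT patient: 2/6 = 33% becomes 1/5 = 20%. The model priors are redacted, so four Beta(a, b) priors for a single dose are assumed. With x DLTs in n patients the posterior is Beta(a + x, b + n − x). The quantity of interest is P(DLT rate ≥ 33%), which the escalation with overdose control (EWOC) rule requires to be below 25%.

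| Assumed prior | 2/6 | 1/5 |
|---|---|---|
| Beta(0.5, 0.5) | 0.53 | 0.29 |
| Beta(1, 1) | 0.58 | 0.36 |
| Beta(0.5, 1.5) | 0.42 | 0.20 |
| Beta(0.32, 1.68) | 0.36 | 0.16 |

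With 2/6 the limit is exceeded under all four priors; with 1/5 it is exceeded under two. The trial's hierarchical model pools over doses and regimens, so these figures show direction only.

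**The case against.** The strongest reply is that this is loose drafting with a clear intent. Table 2-2 sits in the next subsection and gives no low-exposure ground for removing a DLT patient. SAP 2.3 itself applies the 28-day observation requirement only to patients without a DLT. That is good evidence of what was meant. It does not repair the definition: whoever builds the DDS flag has two SAP statements that disagree, and nothing in the public SAP says which prevails.

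A second reply is that escalation is governed by the protocol. Sections 10.1.4, 10.4.2 and 6.2.3.2 set evaluability, and 6.2.3.2 stops enrolment to a cohort after two DLTs whatever the DDS status. In the 2/6 example, crossing the EWOC line would therefore not by itself permit escalation. The SAP is also dated May 2019, three years after the first patient visit in April 2016, and the patient's events would still appear in the Safety Set summaries. All of this stands. It confines the exposure mainly to the DDS outputs in SAP 2.9.2.1 and to any use of the SAP in declaring the MTD or RDE.

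A third reply concerns missed visits. A continuing DLT patient without the Day 8 or Day 15 data named in SAP 2.3 might also fail the first route. But the SAP words those visits as enough for sufficiency, not as the only way to reach it, and protocol 6.3.1 keeps the visit schedule running during an interruption. This route is possible but weaker than the exposure route.

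**Conclusion.** The concern holds. SAP 2.3 is narrower than protocol 10.1.4 and 6.2.3.2 and disagrees with the legible part of SAP Table 2-2. Under QD, the affected patient has a Cycle 1 DLT, misses at least 7 of 27 doses and resumes. One continuous interruption of 7 to 21 days starting on Day 3 to Day 22 is enough.

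The textual conflict is certain; its practical size is not. Such patients are probably few, and their number cannot be estimated because the DLT criteria and Table 6-4 are not in the public text. The conclusion takes "discontinue" in the glossary's sense of a permanent stop. The posterior figures rest on assumed priors and a single dose, and the conclusion does not depend on them. The clause should be corrected because it touches a primary endpoint and errs towards understating toxicity.

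**What to change.** In SAP 2.3, replace the discontinuation clause of the DDS definition with the protocol 10.1.4 wording, "or experienced a DLT during the first 28 days of dosing". Then check that the DDS flag in the Programming Datasets Specifications, which are not public, follows the same rule. The legible part of Table 2-2 already agrees and needs no change on this point.

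The cost is one line of SAP text and a check of one derived variable. No extra data or patients are needed, and no dosing or clinical rule changes. The reported DLT rate may come out slightly higher than under the current wording.
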